5.5 Preparation and Method of Administration

For more information on the method of administration of *Wilate*, please see the European Summary of Product Characteristics or the US Prescribing Information.

Throughout the study, several batches of *Wilate* will be used, and these will be recorded in the clinical study report.

5.6 Blinding, Emergency Envelopes, and Breaking the Study Blind

Not applicable.

5.7 Treatment Compliance

5.7.1 Drug Dispensing and Accountability

Any IMP provided to the site will be accounted for. This includes IMP received at the site, IMP dispensed to patients, and used or unused IMP returned by patients.

A Drug Inventory and Dispensing Log will be kept current by the investigator, detailing the dates and quantities of IMP received and dispensed to each patient and the remaining quantity. The inventory and dispensing log will be available to the monitor to verify drug accountability during the study.

Unused IMP can be destroyed at the study site or returned to the Sponsor for destruction. Destruction can be initiated only after accountability has been verified and fully reconciled by the monitor and after the Sponsor has granted written approval of destruction.

5.7.2 Assessment of Treatment Compliance and Adherence with Infusion Regimen

For all IVR assessments as well as for the PK assessment in paediatric patients, *Wilate* will be administered at the study site, with compliance under the control of the investigator.

Assessment of Adherence with the Infusion Regimen

Throughout the study, adherence with the infusion regimen will be assessed. Any change of the prophylactic dose as determined by the Principal Investigator during the Baseline Visit will be documented in the patient records and eCRF, including start and end dates of each dose, reasons for dose change, or reasons for not implementing a required dose change.

6 STUDY CONDUCT

The flow charts of assessments for prophylactic treatment by study visit are given on **pages 23** and **25**. The flow chart of assessments for surgical prophylaxis is given on **page 27**. Details on the individual assessments and methods are provided in **Section 7**.

6.1 Observations by Visit for Prophylactic Treatment

Because all paediatric patients enrolled in the study will undergo PK assessment, whereas adult patients will not, the first two study visits differ between these two age cohorts.

All enrolled patients will participate in the following study visits:

- Screening Visit
 - For adult patients
 - For paediatric patients
- Baseline Visit
 - Baseline IVR Visit for adult patients
 - Baseline PK Visit for paediatric patients
- 1-Month IVR Visit
- 2-Month IVR Visit
- 3-Month IVR Visit
- 6-Month IVR Visit
- 9-Month IVR Visit
- Study Completion (12-Month) Visit

Between the 3- and 6-Month Visits, the 6- and 9-Month Visits, and the 9- and 12-Month Visits, **monthly telephone contacts** will be performed.

Where needed, **external home-care companies** with experience in conducting clinical trials will be contracted, with trained nurses supporting patients by providing training, re-training, and oversight through home-care visit support throughout the study.

SCREENING AND BASELINE VISITS FOR ADULT PATIENTS (≥ 17 YEARS)

6.1.1 Screening Visit (Adult Patients)

The Screening Visit should take place **at least 72 hours** from the patient's latest administration of a VWF-containing product.

The following assessments will be performed:

- **Obtaining voluntarily given, written (signed and dated) informed consent**
- **Inclusion and exclusion criteria**
- **Demographic and baseline characteristics**
- **Weight**
- **Height**
- **Medical history, including:**
 - VWD type
 - Prior medications
 - Birth control measures (for female patients of child-bearing potential)
 - History of heavy menstrual bleeding (for female patients)
- **Family history of VWD**
- **Vital signs**
- **Physical examination**
- **Blood samples** for the following assessments:
 - AB0 blood group, unless derivable from the baseline characteristics [local lab]
 - Routine safety laboratory [local lab]
- **Urine pregnancy test** (in female patients of child-bearing potential)
- **Concomitant medications**

During the Screening Visit, patients will also receive a patient diary. The investigator will explain to the patient how to fill in the diary and emphasize the importance of carefully documenting any BEs, treatment details, AEs, and concomitant medications. Menstrual bleeds will be documented in the **Pictorial Blood Loss Assessment Chart (PBAC)**. Therefore, female patients of child-bearing potential will also be instructed in completing the **PBAC** (see **Section 7.2.8**).

After the Screening Visit, eligible patients will participate in the Baseline IVR Visit, during which the first prophylactic dose of *Wilate* will be administered.

For adult patients, the Screening Visit and the Baseline IVR Visit **may coincide**; however, note that administration of the first prophylactic dose of *Wilate* during the Baseline IVR Visit requires a **washout period of at least 72 hours** from the patient's previous administration of a VWF-containing product. If possible, the interval between the Screening Visit and the Baseline IVR Visit **should not exceed 2 weeks**.

Between the Screening Visit and the Baseline IVR Visit, on-demand treatment of BEs or prophylactic treatment should be continued with the **patient's previously used VWF-containing product**. Any BEs occurring between the Screening Visit and the Baseline IVR Visit will be **documented in the patient diary (menstrual bleeds in the PBAC)**. Also, any infusions with the patient's previous VWF-containing product during this time will be **documented in the patient diary as concomitant medication**.

6.1.2 Baseline IVR Visit (Adult Patients)

During the Baseline IVR Visit, the prophylactic dose and dosing interval of *Wilate* for each adult patient will be determined by the Principal Investigator based on the patient's clinical condition, and the first prophylactic dose will be administered after a washout period of **at least 72 hours** from the patient's latest administration of a VWF-containing product. Patients must not be experiencing any bleeding.

The following assessments will be performed:

BEFORE ANY OTHER ASSESSMENTS

- **Confirm inclusion and exclusion criteria** (to be documented in patient records)
- **QoL questionnaires** (PROMIS-29 for all patients, SF-36v2 or SF-10 as applicable)

BEFORE INJECTION

- **Weight**
- **Blood samples**
 - VWF multimer pattern for VWD type 2A and genotype for VWD type 2B [central lab]
 - Anti-parvovirus B19 antibodies [central lab]
 - Retention samples for possible virus marker and VWF/FVIII inhibitor testing [central lab]

WITHIN 60 MIN BEFORE AND 60±5 MIN AFTER INJECTION

- **Vital signs**
- **Blood samples**
 - VWF:Ac (VWF:RCO and VWF:GPIb) for IVR [central lab]
 - FVIII:C (OS and CHR) for IVR [central lab]

ANY TIME

- **Patient diary review, with documentation of PBAC** data and calculation of PBAC score by investigator (in female patients of child-bearing potential)
- **Hemophilia Joint Health Score (HJHS)**
- **Target joint(s)**
- Re-confirm commitment to using **birth control measures** (in female patients of child-bearing potential)
- Monitoring of **adverse events (AEs)**
- **Concomitant medications**

In adult patients, the first prophylactic injection of *Wilate* is administered during the Baseline IVR Visit.

In case of **home treatment**, patients will be trained in how to correctly administer the IMP and provided with IMP. Patients will be re-supplied with IMP whenever necessary during the study.

SCREENING AND BASELINE VISITS FOR PAEDIATRIC PATIENTS (6–16 YEARS)

6.1.3 Screening Visit (Paediatric Patients)

The following assessments will be performed:

- **Obtaining voluntarily given, written (signed and dated) informed consent**
- **Inclusion and exclusion criteria**
- **Demographic and baseline characteristics**
- **Weight**
- **Height**
- **Medical history, including:**
 - VWD type
 - Prior medications
 - Birth control measures (for female patients of child-bearing potential)
 - History of heavy menstrual bleeding (for female patients)
- **Family history of VWD**
- **Vital signs**
- **Physical examination**
- **Blood samples for the following assessments:**
 - AB0 blood group, unless derivable from the baseline characteristics [local lab]
 - Routine safety laboratory [local lab]
 - VWF multimer pattern for VWD type 2A and genotype for VWD type 2B [central lab]
 - VWF:Ac (VWF:RCo and VWF:GPIbm) [central lab]
 - FVIII:C (OS and CHR) [central lab]
 - Anti-parvovirus B19 antibodies [central lab]
 - Retention samples for possible virus marker and VWF/FVIII inhibitor testing [central lab]
- **Urine pregnancy test** (in female patients of child-bearing potential)
- **Concomitant medications**

During the Screening Visit, patients will also **receive a patient diary**. The investigator will explain to the patient how to fill in the diary and emphasize the importance of carefully documenting any BEs, treatment details, AEs, and concomitant medications. Menstrual bleeds will be documented in the **Pictorial Blood Loss Assessment Chart (PBAC)**. Therefore, female patients of child-bearing potential will also be instructed in completing the **PBAC** (see **Section 7.2.8**).

After the Screening Visit, eligible children will participate in the Baseline PK Visit. The Screening Visit and the Baseline PK Visit **must not occur on the same day**. If possible, the interval between the Screening Visit and the Baseline PK Visit **should not exceed 2 weeks**.

Between the Screening Visit and the Baseline PK Visit, on-demand treatment of BEs or prophylactic treatment should be continued with the **patient's previously used VWF-containing product**. Any BEs occurring between the Screening Visit and the Baseline PK Visit will be **documented in the patient diary (menstrual bleeds in the PBAC)**. Also, any infusions with

the patient's previous VWF-containing product during this time will be **documented in the patient diary as concomitant medication**.

6.1.4 Baseline PK Visit (Paediatric Patients)

During the Baseline PK Visit, paediatric patients will receive *Wilate* at a dose of 60 ± 10 IU/kg after a washout period of **at least 72 hours** from the patient's previous administration of a VWF-containing product. Patients must not be experiencing any bleeding.

The following assessments will be performed:

BEFORE ANY OTHER ASSESSMENTS

- **Confirm inclusion and exclusion criteria (to be documented in patient records)**
- **QoL questionnaires** (PROMIS-29 for all patients, SF-36v2 or SF-10, as applicable)

BEFORE INJECTION

- **Weight**

WITHIN 60 MIN BEFORE AND 60 ± 5 MIN AFTER INJECTION

- **Vital signs**

WITHIN 60 MIN BEFORE AND 60 ± 5 MIN, 3 ± 30 MIN, 9 ± 1 H, 24 ± 2 H, 48 ± 2 H, and 72 ± 2 H AFTER INJECTION

- **Blood samples**
 - VWF:Ac (VWF:RCO) for PK [central lab]
 - FVIII:C (OS and CHR) for PK [central lab]

ANY TIME

- **Patient diary review, with documentation of PBAC data and calculation of PBAC score by investigator (in female patients of child-bearing potential)**
- **Hemophilia Joint Health Score (HJHS)**
- **Target joint(s)**
- Re-confirm commitment to using **birth control measures** (in female patients of child-bearing potential)
- Monitoring of **adverse events (AEs)**
- **Concomitant medications**

During this visit, the prophylactic dose and dosing interval of *Wilate* will be determined by the Principal Investigator based on the patient's clinical condition.

In paediatric patients, the first prophylactic injection of *Wilate* is administered after the Baseline PK Visit.

In case of **home treatment**, patients will be trained in how to correctly administer the IMP and provided with IMP. Patients will be re-supplied with IMP whenever necessary during the study.

**After the Baseline IVR Visit in adults and the Baseline PK Visit in children,
all subsequent visits will be the same for both age cohorts.**

SUBSEQUENT VISITS FOR ALL PATIENTS

6.1.5 1-Month IVR Visit

The 1-Month IVR Visit will take place 1 month (± 1 week) after the first prophylactic injection of *Wilate*.

During this visit, a prophylactic injection of *Wilate* will be administered. Patients should arrive at the centre within 3 hours before their next planned prophylactic dose. Patients must not be experiencing any bleeding.

The following assessments will be performed:

BEFORE INJECTION

- **Weight**
- **Blood samples**
 - For VWF and FVIII inhibitor testing, *only if* inhibitor development is suspected

WITHIN 60 MIN BEFORE AND 60 \pm 5 MIN AFTER INJECTION

- **Vital signs**
- **Blood samples**
 - VWF:Ac (VWF:RCo and VWF:GP1bM) for IVR [central lab]
 - FVIII:C (OS and CHR) for IVR [central lab]

ANY TIME

- **Patient diary review, with documentation of PBAC** data and calculation of PBAC score by investigator (in female patients of child-bearing potential)
- **Review of compliance** and adherence to the infusion regimen
- Re-confirm commitment to using **birth control measures** (in female patients of child-bearing potential)
- Monitoring of **adverse events (AEs)**
- **Concomitant medications**

At the end of this and each of the following visits, IMP for home treatment will be given to patients as applicable.

6.1.6 2-Month IVR Visit

The 2-Month IVR visit will take place 2 months (± 1 week) after the first prophylactic injection of *Wilate*.

During this visit, a prophylactic injection of *Wilate* will be administered. Patients should arrive at the centre within 3 hours before their next planned prophylactic dose. Patients must not be experiencing any bleeding.

The following assessments will be performed:

- **Same assessments are for the 1-Month IVR Visit**

6.1.7 3-Month IVR Visit

The 3-Month IVR Visit will take place 3 months (± 1 week) after the first prophylactic injection of *Wilate*.

During this visit, a prophylactic injection of *Wilate* will be administered. Patients should arrive at the centre within 3 hours before their next planned prophylactic dose. Patients must not be experiencing any bleeding.

The following assessments will be performed:

- **Same assessments as for the 1-Month IVR Visit**
- **Urine pregnancy test** (in female patients of child-bearing potential)

6.1.8 6-Month IVR Visit

The 6-Month IVR Visit will take place 6 months (± 2 weeks) after the first prophylactic injection of *Wilate*.

During this visit, a prophylactic injection of *Wilate* will be administered. Patients should arrive at the centre within 3 hours before their next planned prophylactic dose. Patients must not be experiencing any bleeding.

The following assessments will be performed:

BEFORE ANY OTHER ASSESSMENTS

- **QoL questionnaires** (PROMIS-29 for all patients, SF-36v2 or SF-10 as applicable)
- **Same assessments as for 1-Month IVR Visit**
- **Urine pregnancy test** (in female patients of child-bearing potential)

6.1.9 9-Month IVR Visit

The 9-Month IVR Visit will take place 9 months (± 2 weeks) after the first prophylactic injection of *Wilate*.

During this visit, a prophylactic injection of *Wilate* will be administered. Patients should arrive at the centre within 3 hours before their next planned prophylactic dose. Patients must not be experiencing any bleeding.

The following assessments will be performed:

- **Same assessments are for the 1-Month IVR Visit**

6.1.10 Study Completion (12-Month) Visit

The Study Completion Visit will take place 12 months (+2 weeks) after the first prophylactic injection of *Wilate*.

During this visit, a prophylactic injection of *Wilate* will be administered. Patients should arrive at the centre within 3 hours before their next planned prophylactic dose. Patients must not be experiencing any bleeding.

The following assessments will be performed:

BEFORE ANY OTHER ASSESSMENTS

- **QoL questionnaires** (PROMIS-29 for all patients, SF-36v2 or SF-10 as applicable)

BEFORE INJECTION

- **Weight**
- **Blood samples**
 - Routine safety laboratory [local lab]
 - For VWF and FVIII inhibitor testing, *only if* inhibitor development is suspected [central lab]
 - Anti-parvovirus B19 antibodies [central lab], *only if* the sample at the Baseline Visit was negative, or if it was equivocal on both original and re-testing

WITHIN 60 MIN BEFORE AND 60±5 MIN AFTER INJECTION

- **Vital signs**
- **Blood samples**
 - VWF:Ac (VWF:RCO and VWF:GPIb) for IVR [central lab]
 - FVIII:C (OS and CHR) for IVR [central lab]

ANY TIME

- **Patient diary review, with documentation of PBAC** data and calculation of PBAC score by investigator (in female patients of child-bearing potential)
- **Review of compliance** and adherence to the infusion regimen
- **Hemophilia Joint Health Score (HJHS)**
- **Target joint(s)**
- **Physical examination**
- **Urine pregnancy test** (in female patients of child-bearing potential)
- **Monitoring of adverse events (AEs)**
- **Concomitant medications**

All used and unused IMP vials will be returned by the patients or their home-care providers.

Patients prematurely withdrawing from the study for any reason will also be invited to attend the Study Completion Visit.

6.1.11 Monthly Telephone Contacts

Monthly telephone contacts will be performed 4, 5, 7, 8, 10, and 11 months (\pm 1 week) after first prophylactic injection of *Wilate*. Should a patient visit the study centre at the time any of these telephone contacts are scheduled, the required assessments may also be performed during this visit.

The following assessments will be performed:

- Review of **compliance** with correctly **completing the patient diary and PBAC** (for female patients of child-bearing potential)
- Review of **adherence with the infusion regimen**
- Monitoring of **adverse events (AEs)**
- **Concomitant medications**

If any issues with completing the diaries or adhering to the infusion regimen are identified, the investigator or home-care provider will re-train the patient accordingly.

6.1.12 Unscheduled Visits and Additional Measures

If inhibitor development is suspected (e.g., based on an unexplained need to increase the dose, a lack of efficacy of IMP injections, or prolonged bleeding), VWF and FVIII inhibitor tests will be performed at the central laboratory and documented (see **Section 7.4.5.1**).

In case of positive inhibitor results, inhibitor retesting using a second, separately drawn sample should be performed, preferably within 15 days of becoming aware of the positive result.

Other reasons for unscheduled visits may be the occurrence of serious AEs or hospitalisations for BEs or surgical interventions.

6.1.13 Surgical Visits

Patients may undergo surgical interventions in the course of the study. Whether or not these patients will be hospitalised will depend on the type and severity of the surgery and be at the discretion of the investigator.

In patients undergoing major surgeries, standard methods of postsurgical thromboprophylaxis, such as gradated compression stockings and early mobilisation, should be used to prevent venous thromboembolism.

For the flow chart of assessments for surgical prophylaxis, see **page 27**.

For details on the surgery data to be documented and the surgical efficacy assessments to be performed, see **Section 7.2.4** and **Section 7.2.5**.

6.2 Duration of Study

6.2.1 Planned Duration for an Individual Patient

The planned treatment duration per patient is 12 months.

6.2.2 Planned Duration for the Study as a Whole

The study will be considered clinically completed when all enrolled patients have completed the planned observation period, including the Study Completion Visit.

The estimated start of the study (enrolment of first patient) is Q2 2020, and the estimated end of the study is Q1 2022.

6.2.3 Premature Termination of the Study

Both the investigator and the Sponsor reserve the right to terminate the study at any time. In this event, any necessary procedures will be arranged on an individual study basis after review and consultation by both parties. In terminating the study, the Sponsor and the investigator will ensure that adequate consideration is given to the protection of the patients' interests.

Regulatory authorities and IECs/IRBs should be informed in accordance with national regulations. Early termination of the study as a whole or by centre may apply for the reasons described below.

6.2.3.1 Early Termination of the Entire Clinical Study

At any time, the study as a whole will be terminated prematurely if new toxicological or pharmacological findings or safety reports invalidate the earlier positive benefit-risk assessment.

6.2.3.2 Early Termination at an Individual Study Centre

At any time, the study can be terminated at an individual centre if:

- The centre cannot comply with the requirements of the protocol.
- The centre cannot comply with GCP standards.
- The required recruitment rate is not met.

Should the study be prematurely terminated, all study materials (completed and partially completed CRFs, IMPs, etc.) must be returned to the Sponsor.

7 ASSESSMENTS AND METHODS

7.1 Demographic and Baseline Information

The following information will be recorded during the Screening Visit (see **Section 6.1.1**):

7.1.1 Demographic and Baseline Characteristics

The demographic and baseline characteristics are age, ethnic origin, weight, height, and AB0 blood group.

7.1.2 Medical History and Prior Medications

The medical history will be obtained by patient interview and by collecting records of past diseases and treatments (e.g., hospital records), if available. Concomitant medications will also be obtained by interview.

For female patients of child-bearing potential, the birth control measures used within 6 months before enrolment will be documented. For all female patients, any history of heavy menstrual bleeding will be recorded. The Pictorial Blood Chart Assessment (PBAC) score calculated during the 6 months previous to Screening will be obtained in an observational study preceding this study, if applicable.

In addition, information about the patients' treatment with VWF-containing product will be collected. To be eligible for the study, complete records on the type, frequency, and treatment of BEs for at least 6 months of on-demand treatment must be available (see **Section 4.1.2**).

The history or (suspected) presence of VWF or FVIII inhibitor activity is an exclusion criterion (see **Section 4.1.3**).

7.2 Efficacy Assessments

This section summarises the assessments to be performed for the calculation of the primary endpoint (see **Section 3.1.1**) as well as the secondary (see **Section 3.1.2**) and exploratory endpoints (see **Section 3.1.3**) of this study.

For details on laboratory analyses, see **Section 7.4.5**.

7.2.1 IMP Administration Data

The following parameters will be documented:

- Dates and times of IMP injections
- Doses of IMP in IU and IU/kg and IMP batch numbers
- Purpose of IMP injection (IVR, prophylaxis, prophylaxis of recurrent bleeding, treatment of BE, surgery, prophylaxis after surgery, or menstrual bleeds)

Injections administered for the purpose of prophylaxis of recurrent bleeding are those injections administered after bleeding cessation and in advance of the patient's next regular prophylactic dose.

7.2.2 Bleeding Episode (BE) Data

Study participants will be instructed by the investigator on recording all BEs and in how to record them. For any BE occurring during the study, the following data will be recorded:

- BE type (spontaneous, traumatic, postoperative, other)
- BE site
- BE severity (minor or major) (see **Table 1**)
- Date and time the BE first occurred or was first noticed
- Date and time the BE ended
- IMP administration data (see **Section 7.2.1**)
- Assessment of the efficacy of treatment at the end of the BE (see **Section 7.2.3**)

All of these parameters will be documented by the patient (together with the investigator in case of on-site treatments or together with the nurse in case a home-care service is used) in the patient diary. Patients who experience a major BE should be treated at the study site, if possible.

Based on these data, the frequency of BEs and the TABR and SABR under prophylactic treatment will be calculated.

If the treatment of a BE in one bleeding site is interrupted for more than 48 hours, two separate BEs will have to be recorded; if, in addition to the original bleeding site, another bleeding site is affected, these events will be recorded as separate BEs at any time.

Menstrual bleedings will not be counted towards the TABR.

BE severity and the severity of menstrual bleeds will be assessed using the criteria given in **Table 1**.

Table 1 Definition of the Severity of Bleeding

Bleeding severity	Description
Minor	Mild haemarthrosis (mild swelling, 'aura,' pain, warmth of the skin over the joint, change in range of motion, decrease in mobility and activity, slight difficulty in using the limb compared with baseline), superficial muscle bleed (pain and/or swelling and functional impairment compared with baseline), soft-tissue bleeding (scrapes, superficial cuts such as those cause by shaving razor, knife, or scissors, bleeding episodes that require frequent bandage changes, cutaneous bleeds with numerous bruises >1 cm), oral bleeding (superficial mouth bleeds, oozing or bleeding related to tooth eruption or extraction, spontaneous or after brushing/flossing, gum bleeding, bleeding after bites to lip or tongue), and most nose bleeds (i.e., those causing distress or interference with daily or social activities).
Major	Generally requires hospitalization; causes incapacity , significant pain, and substantial decrease in range of motion of affected joint (in case of joint bleeds); includes symptomatic bleeding in a critical area or organ (such as intracranial, intraspinal, intraocular, retroperitoneal, intraabdominal, intraarticular, or pericardial bleeds), intramuscular bleeds with compartment syndrome, bleeds of the pelvic muscles, periorbital bleeds, gastrointestinal bleeds, central nervous system bleeds, heavy menstrual bleeding,* bleeding in the area of the neck or throat or pharynx, other major trauma, or bleeding causing a decrease in haemoglobin levels by 20 g/L (1.24 mmol/L) or more. *Heavy menstrual bleeding is any menstrual bleeding that impedes the ability to perform daily activities such as work, housework, exercise, or social activities during menstrual periods and should be considered 'major.' Criteria for heavy (i.e., major) menstrual bleeding may also include any of the following: changing pads/tampons more frequently than hourly; menstrual bleeding lasting 7 or more days; and the presence of clots >1 cm combined with a history of flooding or a PBAC score ≥ 185 .

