5.4 Dose and Dosing Schedule

5.4.1 *Wilate* Dosage for PK Assessment in Paediatric Patients

For the PK assessment in paediatric patients (6–16 years), a single dose of 60 ± 10 IU/kg will be administered.

5.4.2 *Wilate* Dosage for Prophylactic Treatment

For prophylactic treatment, *Wilate* should be administered 2–3 times per week at a dose of 20–40 IU/kg BW for 12 months.

The prophylactic dose for each patient will be determined by the Principal Investigator based on each patient's clinical condition and at the following time points:

- At the Baseline IVR Visit (see Section 6.1.2) in adult patients (≥ 17 years)
In adult patients, the first prophylactic dose will be administered at the time of the baseline IVR assessment.
- At the Baseline PK Visit (see Section 6.1.4) in paediatric patients (6–16 years)
In paediatric patients, the first prophylactic dose will be administered after completion of the PK phase.

In case of unacceptably frequent spontaneous breakthrough BEs (i.e., more than 2 spontaneous BEs or 1 major spontaneous BE within a 30-day period), the dose of *Wilate* should be increased by approximately 5 IU/kg (depending on the entire content of the additional vials that need to be reconstituted). If, after a dose increase, patients still experience more than 2 spontaneous bleeding episodes, the dosing interval should be shortened from 2 times per week to 3 times per week.

5.4.3 *Wilate* Dose for the Treatment of Breakthrough BEs

The dose (and duration) of treatment of BEs will depend on the location and extent of bleeding and on the clinical condition of the patient.

Generally, 1 IU/kg BW VWF:Ac (VWF:RCo) and FVIII:C raises the plasma level by 1.5–2% of normal activity for the respective protein. Usually, about 20–50 IU *Wilate*/kg BW are necessary to achieve adequate haemostasis. This will raise the VWF:Ac (VWF:RCo) and

FVIII:C in the patients by approx. 30–100%.

The following should be used to guide dosing in the treatment of BEs:

Dose type	Minor haemorrhage*	Major haemorrhage
Loading dose	20–40 IU/kg	40–60 IU/kg
Maintenance dose	20–30 IU/kg every 12–24 hours	20–40 IU/kg every 12–24 hours
Therapeutic goal	Maintain VWF:Ac (VWF:RCo) and FVIII:C trough levels >30%	Maintain VWF:Ac (VWF:RCo) and FVIII:C trough levels >50%

*Menstrual bleeds of regular intensity (i.e., minor menstrual haemorrhage) will be considered normal and are not expected to require therapy unless deemed necessary by the investigator and/or the patient.

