7.2.3 Efficacy of the Treatment of Breakthrough BEs

At the end of a BE, treatment efficacy will be assessed by the patient (together with the investigator in case of on-site treatment) using the predefined criteria detailed in **Table 2**.

Table 2 Efficacy Assessment of the Treatment of Breakthrough BEs

Excellent	Bleeding was completely stopped within 3 days in case of minor bleeds, within 7 days in case of major bleeds, and within 10 days in case of gastrointestinal bleeds
Good	Bleeding was completely stopped, but time and/or dose slightly exceeded expectations
Moderate	Bleeding could be stopped only by significantly exceeding time and/or dose expectations
None	Bleeding could be stopped only by using other VWF-containing products

The **proportion of BEs successfully treated with IMP** will be evaluated for all BEs taken together and by BE severity. All efficacy ratings assessed as either 'excellent' or 'good' will be considered 'successfully treated.'

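### Table 1 puts a mild symptomatic joint bleed in both the minor and the major row, and no rule says which row prevails

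*Protocol*

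**What the plan says.** Three entries in Protocol 7.2.2, Table 1, bear on joint bleeds:

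- **Minor row:** "Mild haemarthrosis (mild swelling, 'aura,' pain, warmth of the skin over the joint, change in range of motion" and further mild signs.
- **Major row, graded test:** the bleed causes incapacity, with "significant pain, and substantial decrease in range of motion of affected joint (in case of joint bleeds").
- **Major row, list of sites:** symptomatic bleeding at a critical site is major, and the examples end with "intraabdominal, intraarticular, or pericardial bleeds", with no grade attached.

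Severity is recorded with the other details of each bleed: "All of these parameters will be documented by the patient", in the diary. The investigator takes part when treatment is on site, and the nurse when a home-care service is used.

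The label is then used elsewhere. Protocol 7.2.3, Table 2, defines *excellent* as "Bleeding was completely stopped within 3 days in case of minor bleeds, within 7 days in case of major bleeds", with a separate limit for gastrointestinal bleeds. Protocol 5.4.2 sets the regimen-change trigger at "more than 2 spontaneous BEs or 1 major spontaneous BE within a 30-day period", and SAP 4.3 repeats it. The guide to treating bleeds in Protocol 5.4.3 has separate minor and major columns. Protocol 7.2.3 and 9.2.2 call for success by severity, and SAP 4.7.3 tabulates bleeding severity.

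**The concern.** A severity scale that feeds an efficacy rating and a treatment trigger should place each bleed in one class. For a mild symptomatic haemarthrosis, two raters can read the same table correctly and record different severities. The label then sets the time limit the bleed is judged against, the table row it appears in, the treatment column that applies, and whether that one bleed is enough to call for a regimen change. Differences between patients or sites in how the table is read would show up as differences in severity mix and in the share rated *excellent*.

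**Working it through.** The plan gives no figure on this point, so there is none to reproduce. The check compares the entries and follows the label through its uses.

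**1. Do the rows overlap?** A haemarthrosis is a bleed into a joint, so it is intraarticular. The minor row describes the mild form by swelling, pain, warmth and altered motion, so it is symptomatic. The site list in the major row asks for nothing more. A mild symptomatic haemarthrosis therefore meets the minor row and the site list. It does not meet the graded test in the major row. A joint bleed with incapacity and substantial loss of motion is major under both major-row entries, so the conflict is confined to the mild form.

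**2. Is there a tie-break?** None appears in Table 1, and SAP 4.7.3 uses minor and major without redefining them. The protocol does write such rules elsewhere. In 7.2.4, any one listed criterion makes a surgery major and all others are minor. Table 1 itself states that heavy menstrual bleeding counts as major.

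**3. Effect on the efficacy rating (Protocol 7.2.3, Table 2).**

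| Bleed stopped | Labelled minor | Labelled major |
|---|---|---|
| Within 3 days | *excellent* | *excellent* |
| After 3 and up to 7 days | *good* at best; *moderate* if the excess is judged significant | *excellent* |
| After 7 days | not *excellent* | not *excellent* |

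The limit differs by a factor of 7/3 = 2.33. *Excellent* and *good* both count as success. In the middle row, success changes only if the rater calls the excess significant rather than slight, and neither word is given a number.

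**4. Effect on the trigger (Protocol 5.4.2).** One such spontaneous bleed in 30 days meets it if labelled major. If every one is labelled minor and there are no other spontaneous bleeds, three are needed.

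The documents give no rate of mild spontaneous joint bleeds, so the following is for scale only. Assume Poisson counts at r per year, so that m = r × 30/365.25. Then P(at least 1) = 1 − e^(−m), and P(at least 3) = 1 − e^(−m)(1 + m + m²/2).

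| Assumed r per year | m | All labelled major: P(at least 1) | All labelled minor: P(at least 3) |
|---|---|---|---|
| 1 | 0.082 | 7.9% | 0.01% |
| 2 | 0.164 | 15.2% | 0.07% |
| 4 | 0.329 | 28.0% | 0.5% |
| 6 | 0.493 | 38.9% | 1.4% |
| 12 | 0.986 | 62.7% | 7.8% |

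These are the two extremes of labelling, per 30-day window. Other spontaneous bleeds also count towards the trigger, so the contrast would be smaller in a patient who has them.

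**5. What does not depend on severity?** The total and spontaneous annualised bleeding rates count bleeds whatever their severity (Protocol 3.1.1 and 3.1.2; SAP 4.7.1 and 6.1). Efficacy in breakthrough bleeds is an exploratory endpoint (Protocol 3.1.3; SAP 4.7.3).

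**The case against.** The strongest reply is that the major row already grades joint bleeds. It opens with a general expectation of hospitalisation and a joint-specific test, against mild swelling and slight difficulty with the limb in the minor row. A sensible rater would apply the specific test before a general list of critical sites. This stands as evidence of intent: it suggests that only severe joint bleeds were meant to be major. It does not remove the conflict, because the ungraded site entry is in the same cell and nothing subordinates it.

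The recording process also has checks. Patients are instructed by the investigator, and major bleeds should be treated on site where possible (7.2.2). Diaries are reviewed and validated by site staff at follow-up visits (8.1.1). A reader might infer from the diary wording that patients' ratings go unchecked; the documents do not support that. The checks are still limited. Section 8.1.1 does not name severity, reviewers work from the same table, and investigator review of severity is spelled out only for menstrual bleeds (7.2.8).

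The label does not decide treatment alone either. Protocol 5.4.3 also refers to the location and extent of bleeding and the patient's condition, and the trigger concerns spontaneous bleeds only. Both limits stand.

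**Conclusion.** Table 1 contradicts itself for mild symptomatic haemarthrosis, and neither document resolves it. For those bleeds the *excellent* limit is 3 or 7 days and the trigger is met by one spontaneous bleed or by more than two, depending on the row chosen. The severity tables and the treatment column move with the label. How many bleeds this touches cannot be stated, because the share of joint bleeds is not given; the trigger percentages rest on assumed rates.

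Three stronger readings are tempting and are not supported:

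- **Every joint bleed is doubly classified.** Clearly severe ones are major on either reading.
- **The success rate by severity cannot be interpreted.** *Good* is still a success, a bleed stopped within 3 days is *excellent* under either label, and the recorded bleed site identifies joint bleeds. The result is ambiguous for mild joint bleeds only.
- **The primary result is compromised.** The bleeding rates ignore severity, so any effect could come only indirectly, through regimen changes.

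This is a minor clarification with a cheap remedy.

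**What to change.** Reconcile the two rows of Table 1 so that any joint bleed meets only one, and state which entry prevails if two seem to apply. The clinical cut-off is for the sponsor's clinicians. The trigger in Protocol 5.4.2 and SAP 4.3 and the guide in Protocol 5.4.3 should be read against the reconciled table.

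For bleeds already recorded, use the recorded site to show joint bleeds as a separate row in the severity and success tables. Beside it, use the recorded start and end times to give the number of joint bleeds stopped within 3 days and within 7 days. Table 2 does not say when its clock starts, so state that the recorded start was used. Moving joint bleeds between the minor and major rows would not be enough, since the original ratings would move unchanged. The elapsed times show directly how many bleeds fall where the label matters for *excellent*; they cannot settle *good* against *moderate*.

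The cost is one wording change and one small extra table, with no new data collection.
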